4.12.2. Safety laboratory data

Laboratory data will be summarized by type of laboratory test after all results are converted to standard SI units (according to algorithms presented in Data Validation Plan). Descriptive statistics will be calculated for each laboratory parameter at baseline (Day 1) and at each scheduled time point. Shift tables using the categories 'lower than normal range', 'within normal range' and 'higher than normal range' will be provided for each numeric parameter, comparing the baseline value to all post-baseline values. For results expressed as category (in urinalysis) shift tables will present categories: normal and abnormal. Moreover, change from baseline values will also be presented.

Other urinalysis parameters, than those pre-specified in the eCRF, will be listed only.

Listings of each laboratory parameter will be provided, marking changes from norm. A separate listings will be produced for clinically significant abnormal results (for purpose of presentation in the statistical report/CSR).

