#### **Intensity**

The Investigator will assess all AEs for severity in accordance with the following standard ratings:

1. Mild: Ordinarily transient symptoms, does not influence the performance of the subject's daily activities. Treatment is not ordinarily indicated;
2. Moderate: Marked symptoms, sufficient to make the subject uncomfortable. Moderate influence on the performance of the subject's daily activities. Treatment may be necessary;
3. Severe: Symptoms cause considerable discomfort. Substantial influence on the subject's daily activities. May be unable to continue in the study and treatment may be necessary.

When changes in the intensity of an AE occur more frequently than once a day, the maximum intensity for the event should be noted for that day. Any change in the severity of signs and symptoms over a number of days will be captured by recording a new AE, with the amended severity grade, and the date (and time, if known) of the change.

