**Pregnancy Testing**

Serum/urine human beta chorionic gonadotrophin (women of childbearing potential only)

---

Any value outside the normal range will be flagged for the attention of the Investigator or qualified designee at the site. The Investigator or designee will indicate whether the value is of clinical significance. If the result of any test (or repeat test, if done) from the samples taken during the Screening Period is indicated as clinically significant, the subject will not be allowed into the study. Additional testing during the study may be done if medically indicated. If a clinically significant abnormality is found in the samples taken after dosing, during the study, and/or at the Follow-up Visits, it should be recorded as an AE and the subject will be followed until the test(s) has (have) normalized or stabilized, at the discretion of the Investigator.

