2.1.2. Secondary endpoints

Clinical Efficacy:

- Proportion of subjects with DAS28-CRP remission at Weeks 4; 8; 12 and 16.
- American College of Rheumatology (ACR)20, ACR 50, ACR 70, and ACR 90 responder rates (Weeks 4, 8 and 12).
- Change from Baseline in the Tender/Painful and Swollen Joint Count (Weeks 4, 8 and 12).
- Change from Baseline in the Physician's Global Assessment (PhGA) of Arthritis (Weeks 4, 8 and 12).

Patient Reported Outcome:

- Change from baseline in the Patient's Assessment of Arthritis Pain (PAAP) VAS and Patient Global Assessment of Arthritis (PtGA, VAS) at Week 4, 8, and 12.
- Change from baseline in the Health Assessment Questionnaire – Disability Index (HAQ-DI) at Week 4, 8, and 12.
- Change from baseline in the SF-36 RAND 8 Domain scores and Physical Component Score (PCS) and Mental component score (MCS) at Week 12.
- Change from baseline in the Functional Assessment of Chronic Illness Therapy Fatigue (FACIT-F) total score at Week 12.

Safety:

Safety and tolerability of CPL409116: vital signs (blood pressure (BP), pulse and temperature), laboratory tests, Adverse Events (AEs) and Serious Adverse Events (SAEs), 12-lead electrocardiogram (ECG):

- Incidence and severity of adverse events, serious adverse events, and withdrawals due to adverse events (Baseline through Week 16).
- Incidence of abnormality in clinical chemistry parameters (Baseline through Week 16).
- Incidence of abnormality in haematological parameters (Baseline through Week 16).
- Change from baseline in blood pressure measurement (Baseline through Week 16).
- Change from baseline in pulse rate measurement (Baseline through Week 16).
- Change from baseline in temperature measurement (Baseline through Week 16).
- Incidences of targeted medical adverse events (Baseline through Week 16).

Pharmacokinetics:

- CPL409116 and metabolite M3 pharmacokinetic variables: $AUC_{(0-6h)}$, C_{max} , T_{max} , $T_{1/2}$ (if possible) and K_{el} (if possible) determined on Day 1, 8, 57 and 85.
- CPL409116 pharmacokinetic variables: C_{0h} , $C_{2.5h}$ determined on Day 29.

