4.12. Safety analyses

Safety data will be summarized for the safety population (SS). Unless otherwise stated, unscheduled visit results will be included in date/time chronological order, within patient listings only.

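### SAP 4.12.2 categorises numeric laboratory safety results only as low, normal or high, with no grades and no worst value per patient

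*SAP*

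**What the plan says.** **Endpoints.** SAP 2.1.2 lists "Incidence of abnormality in clinical chemistry parameters (Baseline through Week 16" and "Incidence of abnormality in haematological parameters (Baseline through Week 16" among the safety endpoints. Neither mentions severity.

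**Laboratory tables.** SAP 4.12.2 plans descriptive statistics at each scheduled time point, change from baseline, and a three-category shift: "Shift tables using the categories 'lower than normal range', 'within normal range' and 'higher than normal range' will be provided for each numeric parameter". The shift compares the Day 1 value with all post-baseline values. SAP 4.3 puts summary tables by treatment group, so these counts are per arm. The only laboratory derivation rule, in SAP 4.2.15, is substitution at the quantification limits.

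**Listings.** SAP 4.12.2 also lists every parameter with out-of-range values marked, and lists clinically significant abnormal results separately. SAP 4.5 puts patient identifier and treatment group on every listing. Under SAP 4.12, unless otherwise stated, "unscheduled visit results will be included in date/time chronological order, within patient listings only".

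**The adverse-event route.** Protocol 8.2, in the text after the table of laboratory tests, says "The Investigator or designee will indicate whether the value is of clinical significance" and that "Additional testing during the study may be done if medically indicated". A clinically significant abnormality after dosing becomes an adverse event. Protocol 8.1 grades intensity by symptoms and daily activities; the top level begins "Severe: Symptoms cause considerable discomfort". SAP 4.12.1 tabulates treatment-emergent events by maximum severity.

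**The concern.** A three-category shift shows whether a value crossed a limit of normal, but not how far beyond it. It places mild and marked abnormalities in the same cell and cannot register a patient who starts high and goes much higher. Without a rule that reduces each patient to one value, it also does not say how many different patients were ever abnormal, which is the natural way to read an incidence from baseline through Week 16.

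Severity of laboratory change is then counted per arm only for abnormalities that the Investigator judged clinically significant and recorded as adverse events, on a scale poorly suited to a symptom-free transaminase rise or neutropenia. At stake is whether a reader comparing three doses with placebo can see from a table how many patients per dose had a marked laboratory change.

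The documents give some reason to look. Protocol 2.2 reports lower white-cell and red-cell values and raised bilirubin in animals. All patients also take methotrexate, and SAP 2.2 names liver and blood toxicity as grounds for a lower methotrexate dose.

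**Working it through.** The plan states no figure on this point, so the check is mainly of the text.

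**1. Can worsening within the high category occur?** Exclusion item 12 (SAP 2.2.1) removes ALT, AST or bilirubin at or above 1.5 x ULN at screening. Values between 1 and 1.5 x ULN are admissible unless a screening result "is indicated as clinically significant, the subject will not be allowed into the study". The shift baseline is Day 1 (SAP 4.2). For illustration, assume a Day 1 ALT of 1.4 x ULN:

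| Day 1 | Later value | Shift cell |
|---|---|---|
| within range | just above ULN | normal to high |
| within range | 6 x ULN | normal to high |
| 1.4 x ULN | 1.4 x ULN | high to high |
| 1.4 x ULN | 6 x ULN | high to high |

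The last row is a 6/1.4 = 4.3-fold rise that the table cannot distinguish from no change.

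**2. Does any other planned table count it?** Descriptive statistics give the mean, quartiles, minimum and maximum at each scheduled visit (SAP 4.3). The maximum shows that an extreme value exists, but not how many patients had one. Boxplots, if used for that parameter, show outliers as points (SAP 4.4). The targeted-event list in SAP 4.2.14 has no liver or blood-count item, although such events would still appear in the general adverse-event tables. CTCAE appears only in the protocol's abbreviation list.

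**3. Is there a patient-level count through Week 16?** Chemistry and haematology are taken at six scheduled post-baseline visits (SAP Table 1, footnote j): Days 8, 29, 57 and 85 on treatment, then Days 99 and 113 in follow-up. SAP 4.12.2 does not say whether the comparison with all post-baseline values means one table per visit or all values pooled. Either way a patient who is high at several visits is counted several times. No rule selects one value per patient.

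**4. Do unscheduled results enter the shift tables?** SAP 4.12 keeps them in listings unless otherwise stated. SAP 4.12.2 limits descriptive statistics to scheduled time points but uses the wider term, all post-baseline values, for the shifts. That may be the exception, or it may not. The text does not settle it.

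**5. What could the added table show at this sample size?** One patient is 1/25 = 4% of an arm. With zero events among n patients, the upper exact two-sided 95% limit is 1 − 0.025^(1/n):

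- n = 25 (one arm as randomised): 13.7%
- n = 21 (one arm after the assumed dropout): 16.1%
- n = 75 (three active arms pooled): 4.8%

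The table would be descriptive and could not exclude uncommon toxicity.

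**The case against.** The strongest reply is that nothing is hidden. Every laboratory value, unscheduled ones included, is listed with patient and arm, and clinically significant results have their own listing. With 25 patients per arm, a reader can count. That stands: what is missing is a ready table, not the data.

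The second reply is that a clinically significant peak should also become an adverse event and be counted by preferred term and maximum severity. This holds only in part, because it depends on the Investigator's judgement and on a symptom-based scale.

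Third, neither document requires grading, and the SAP goes beyond Protocol 10.7, which asks for shift tables only for selected parameters. That also stands. A reader might infer that the SAP contradicts its own endpoint. It does not: the endpoint promises incidence of abnormality, without severity and without saying that it is cumulative, and low/normal/high counts per arm are one measure of it.

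Fourth, the animal findings came largely at high doses. In dogs, raised bilirubin and lower red-cell values appeared at 120 mg/kg/day, against a no-adverse-effect level of 30. In rats, white cells fell from 30 mg/kg/day and red-cell values at 100, and both were comparable to controls after recovery. Methotrexate is background treatment in every arm. These facts support a routine check; they do not establish an expected human signal.

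**Conclusion.** The gap is real but modest. Numeric laboratory results have no graded or ULN-multiple categories and no worst value per patient. Worsening within high is therefore absent from the shift tables, and the number of patients per arm ever abnormal through Week 16 must be compiled by hand or inferred from adverse events. Whether unscheduled values enter the shifts is unclear and needs a sentence either way.

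Two stronger readings should be resisted. One is that a reader cannot see marked changes, or that a peak on an unscheduled test disappears; the listings rule that out. The other is to size the problem by bounding the number ever high from visit-by-visit counts. Such a range needs an assumed count per visit, reaches its upper end only if different patients are affected at every visit, and says nothing about grade. It is not a measure of this gap.

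The point affects safety presentation only; the primary endpoint, its test and the sample size do not change. It is an optional improvement. The ALT example is an assumed case, chosen to fit the entry limit.

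**What to change.** Keep the existing tables. Before unblinding, add to SAP 4.12.2:

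- By-arm shift tables from baseline to worst post-baseline value through Week 16, expressly including unscheduled and early-withdrawal results, optionally repeated for values through Day 85 only. Cover haemoglobin, white cells, neutrophils, lymphocytes, platelets, ALT, AST, bilirubin, CK and creatinine, by CTCAE grade or by fixed limits written into the SAP, with the direction that counts as worst stated for each.
- A per-arm count of patients with ALT or AST raised together with bilirubin, at ULN multiples stated in the SAP.
- One sentence saying whether unscheduled results enter the existing low/normal/high shifts.

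All values are already collected, so the cost is SAP wording and a few tables. The downside is sparse cells at 25 per arm and slightly more output. Fixing the limits before unblinding also avoids choosing them after the results are known.

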4.12.3. Vital signs

These summaries will take form of tables for raw data and changes from baseline (Day 1) as well as percentage of abnormal values.

Shift tables using the categories 'lower than normal range', 'within normal range' and 'higher than normal range' will be provided for each parameter (where applicable), comparing the baseline value to all post-baseline values. Categorization of blood pressure is performed for both SBP and DBP at once, so one shift table will be prepared only for blood pressure.

Change from baseline values in vital signs will take form of boxplots (and/or point and whisker plots) for each study arms for each vital sign parameter.

Listings flagging abnormal values will be also produced.

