4.4. Specifications for plots

Unless otherwise specified, plots for continuous variables will present mean and SD for each randomized treatment group. LS means calculated from MMRM models will be presented as bars with whiskers representing 95% confidence intervals (CI). Binary endpoints will be presented as forest plots – with a point representing proportion of subjects meeting the endpoint and whiskers representing a 95% CI. Results from logistic regression will also take form of a forest plot – point with whiskers, where point represents odds ratio and whiskers confidence interval.

Time to remission will be presented graphically using Kaplan-Meier curve – a series of declining horizontal steps.

For safety analysis distribution of data will be presented as line and point and whisker plots (presenting mean and standard deviations) or boxplots (for variables with highly skewed distributions – such as CRP). For boxplot top and bottom of the box will represent lower and upper quartile respectively. Thick line in the middle of the box will be median. Whiskers will represent the lowest value at most $Q1+1,5*IQR$ (inter quantile range) and the largest value no further than $Q3+1,5*IQR$. Points will represent potential outliers. Treatment groups will be presented as separate panels within a figure.

Data will be shown for each randomized treatment group. Data collected during unscheduled visit will not be shown on plots unless otherwise specified.

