4.8. Demographic and baseline variables

Demographic data and other baseline characteristics will be summarized for Safety, FAS, ITT and PP population by treatment group and overall. Separate tables for Safety and ITT populations will be prepared when number of patients in those populations will differ from FAS population. The following variables will be summarized:

- Age (years) as continuous variable [(date of ICF signature – date of birth)/365.25]
- Age category (<57/ ≥57 years old)
- Sex (male / female)
- Race
- Weight [kg] and height [cm]
- BMI [kg/m²] calculated as Weight (kg)/[height (m)²]
- BMI categories (Underweight/ Normal weight/ Overweight/ Obese)
- History of plasma donation (yes / no)
- History of blood donation (yes / no)
- Use of special diet (yes / no)

A separate table will summarize a history of alcohol and drug abuse and substance use history:

- History of alcohol abuse (yes / no)
- History of drug abuse (yes / no)
- Smoking (Never, Current, Former, Not collected)
- Amount of cigarettes smoked [pack-years]
- Amount of coffee consumed [cups]
- Amount of tea consumed [cups]
- Amount of energy drinks consumed [cans].

Disease characteristic will summarize:

- Duration of rheumatoid arthritis (years)
- Duration of methotrexate treatment (years)
- Tender (68) and swollen (66) joints
- DAS28-CRP assessment from screening and Day 1 baseline including disease activity categorization.

A separate table will summarize results on rheumatoid biomarkers indicators collected during screening and Day 1 baseline.

Total scores, collected during baseline, will be summarized in a table for following scales:

- Physician Global Assessment of Arthritis (PhGA)
- Patient's Global Assessment of Arthritis (PtGA)
- Patient Assessment of Arthritis Pain (PAAP)
- Health Assessment Questionnaire – Disability Index (HAQ-DI) including pain level measured with VAS.

Due to size a separate table will present subscales of 36-Item Short Form Survey Instrument (SF-36) and total score from Functional Assessment of Chronic Illness Therapy – Fatigue (FACIT-F).

Separate tables will be produced for screening and baseline safety data:

- Vital signs: blood pressure [mmHg], heart rate [beats per minute], body temperature [°C] (numerical results as well as categorization of result)

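### One joint SBP/DBP category and a single shift table lose part of the blood pressure shift information; separately, the boxplot rule in SAP 4.4 has a sign error

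*SAP*

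**What the plan says.** SAP 4.12.3 opens with a general rule: "Shift tables using the categories 'lower than normal range', 'within normal range' and 'higher than normal range' will be provided for each parameter (where applicable"). It then makes an exception for blood pressure: "Categorization of blood pressure is performed for both SBP and DBP at once, so one shift table will be prepared only for blood pressure". SAP 4.8 also uses a vital-sign category at baseline, asking for "numerical results as well as categorization of result". No section of either document states the blood pressure limits or the rule for a reading whose SBP and DBP fall in different categories.

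The endpoint itself is numeric. SAP 2.1.2 lists "Change from baseline in blood pressure measurement (Baseline through Week 16") among the secondary safety endpoints.

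SAP 4.4 defines the boxplots used for safety data. On the lower end it says "Whiskers will represent the lowest value at most" Q1 + 1.5×IQR, with a plus sign; the upper limit is Q3 + 1.5×IQR. It adds: "Points will represent potential outliers". The same paragraph assigns the lower quartile to the top of the box and the upper quartile to the bottom.

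**The concern.** A shift table shows how many patients in each arm moved from one category to another. With a single label for two measurements, a patient whose SBP stays high can look unchanged although DBP has moved down a category. A pair with one component high and the other low has no obvious label, so the table cannot be reproduced from the plan. The percentage of abnormal values and the abnormal flags in the listings would inherit this ambiguity if they use the same category.

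Downward change is of particular interest here. SAP 4.2.14 makes hypotension and abnormal blood pressure targeted adverse events, and Protocol 2.1 links the ROCK pathway, which the drug inhibits, to contraction of smooth muscle. With 25 patients randomised per arm, individual shifts carry weight.

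The whisker rule raises a smaller, separate question: whether a boxplot drawn to the letter of SAP 4.4 would mark an unusually low value.

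**Working it through.** The plan gives no figure for the size of the first issue, so there is none to reproduce. For the second, the plan's own formula can be checked directly.

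**1. States lost by joint classification.** Three SBP categories × three DBP categories = 9 states, reported as 3. In 3 states the components agree; in 9 − 3 = 6 they differ. Of those 6, 4 have one component within range and 2 have the components in opposite directions.

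**2. How a move is masked.** Suppose SBP is high at both visits and DBP goes from high to within range. If the joint label is high whenever either component is high, it is high at both visits. If low takes precedence instead, no component is low, so the label is again high at both visits. The DBP move is absent under both rules.

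**3. Possible size.** All inputs are assumptions, because the documents give none:
- baseline SBP 135 (SD 16) and DBP 80 (SD 10) mmHg, bivariate normal, with the same SDs at follow-up;
- SBP–DBP correlation 0.4, 0.6 or 0.7; baseline to follow-up correlation 0.6;
- limits 90/140 for SBP and 60/90 for DBP;
- mean change in (SBP, DBP) of (0, 0), (−5, −5) or (−3, −8) mmHg;
- 400,000 simulated patients per scenario.

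| Quantity | High takes precedence | Low takes precedence |
|---|---|---|
| Baseline readings with SBP and DBP in different categories | 29–36% | 29–36% (does not depend on the rule) |
| Of patients with a downward SBP or DBP category move, share with no downward joint move | 17–25% | 16–25% |
| Of patients with a newly low SBP or DBP, share not labelled low | about 0.3–10% | 0, by definition |

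Most masked moves are from high to normal. The share masked is nearly the same under the two rules, so it comes from the collapse and not from the choice between these two. Other rules were not examined.

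**4. Whisker limit.** Since Q3 = Q1 + IQR, Q1 + 1.5×IQR = Q3 + 0.5×IQR. That lies above the box and cannot be a lower limit. For normal data it is the mean + 1.35 SD, with 91% of values below it. The conventional Q1 − 1.5×IQR is the mean − 2.70 SD, with 0.35% below.

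The minimum never exceeds Q1, and Q1 never exceeds Q1 + 1.5×IQR. The lowest value at or under the printed limit is therefore always the minimum.

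Assumed example: 25 changes, one of −40 mmHg, with Q1 = −5, Q3 = 6 and IQR = 11.
- Conventional limit: −5 − 16.5 = −21.5. The whisker ends at −12 and −40 is a separate point.
- As printed: −5 + 16.5 = 11.5. The whisker ends at −40 and no point is drawn.

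In 20,000 simulated normal samples per size, with one patient set to a 4-SD fall, the conventional rule marks that patient in about 96% of samples at n = 25 and 95% at n = 21. The printed rule marks no low value in any sample.

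**The case against.** A reader might infer that these displays hide falls in blood pressure. The documents do not support that, for four reasons.

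- Under the printed whisker rule the largest fall is still drawn, at the end of the whisker; only its outlier mark is lost. SAP 4.12.3 also allows point-and-whisker plots for vital signs, and SAP 4.4 intends safety boxplots for highly skewed variables, so blood pressure may never be shown as a boxplot.
- Falls are reported elsewhere. SAP 4.12.3 plans tables of raw values and of change from baseline, and SAP 4.3 puts the minimum and quartiles in such summaries, so the largest fall per arm and visit is shown. SAP 4.12.3 adds listings that flag abnormal values. Protocol 10.7 lists observed values and changes for each subject, and SAP 4.5 puts the treatment group in every listing.
- SAP 4.12.1 compares the incidence of targeted events, which include hypotension, between arms with 95% confidence intervals.
- Even separate shift tables would miss a large fall that stays within the normal range.

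All of this stands, as does the point that the percentages in the working rest on assumed inputs. It does not settle the narrower issue. Listings do not tabulate shifts by arm, and group summaries do not show how many patients changed category. The SAP's stated reason for one table is only that the category is joint, and the rule behind that category is missing.

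**Conclusion.** The point holds as a minor one. The joint category discards shift information and leaves the table undefined for discordant pairs. Its likely size, about 16–25% of patients with a downward component move, depends on the assumed limits, distributions and the two assignment rules tried. It should not be read as concealment of hypotension: even with high taking precedence, at most about 10% of patients with a newly low component lose the low label. The primary analysis is untouched.

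The sign error in SAP 4.4 is certain from the algebra. It applies to every boxplot drawn under that section, is not specific to blood pressure, and affects how low values are marked rather than whether they are seen.

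**What to change.** - **SAP 4.12.3:** derive separate SBP and DBP categories from the numeric values already collected, using limits pre-specified and stated in the SAP. Give two shift tables and two percentage-abnormal rows. If a joint category is kept as well, state its rule for discordant pairs.
- **SAP 4.4:** define the lower whisker as the lowest value not below Q1 − 1.5×IQR, and state that the bottom of the box is Q1 and the top is Q3.

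The cost is one extra shift table, the wording changes, and agreement on the limits, which the documents do not now give. No new data are needed.
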